#### 10.1.5 Serious Adverse Events

## 10.1.5.1 Definition of a Serious Adverse Event

Any untoward medical occurrence that:

- Results in death
- Is life-threatening
- Requires inpatient hospitalization or prolongation of existing hospitalization
- Results in persistent or significant disability/incapacity
- Is a congenital anomaly/birth defect
- An important medical event which requires medical intervention to prevent any of the above outcomes

The term "life-threatening" refers to an event in which the patient was at risk of death at the time of the event; it does not refer to an event which hypothetically might have caused death if it were more severe.

The term "Inpatient hospitalization" or prolongation of existing hospitalization means that the event required at least 24 hours hospitalization and/or prolongation of hospital stay were required for treatment of AE, or that they occurred as a consequence of the event.

The term "Important medical event" are those which may not be immediately life-threatening but may jeopardize the subject and may require intervention to prevent one of the other serious outcomes listed above. Examples of such events are intensive treatment in an

emergency room or at home for allergic bronchospasm; blood dyscrasias or convulsions that do not result in hospitalization.

### 10.1.5.2 Expectedness

The expectedness of an AE is defined in accordance with the Reference Safety Information. For a detailed description refer to the current IB.

An unexpected AE is an AE for which the nature or severity is not consistent with the Reference Safety Information.

### 10.1.5.3 SAE Reporting

The Sponsor is required to expedite to regulatory authorities reports of specific SAEs that occur during the study. SAEs must be reported to the Sponsor (or its designee) by the Investigator/site personnel as soon as they become aware of the event and no later than 24 hours regardless of relationship to the study drug.

SAE report form completion and reporting must not be delayed even when information is incomplete at the time of the initial report.

Any additional (follow-up) information that becomes available after the initial reporting, should be forwarded in a follow-up SAE report form by the site personnel within 24 hours of the information becoming available.

All SAEs should be reported to Sponsor or its designee following the completion guidelines provided with the study SAE form. All SAEs should be followed until resolution or stabilization and all parameters (including laboratory) return to baseline or until the Investigator assesses them as stable or until the patient is lost to follow-up. SAEs must be collected and reported during the study and up to 30 days after study completion. The Investigator does not need to actively monitor subjects for AEs once the study has ended, but SAEs occurring to a patient should be reported to the Sponsor, if the Investigator becomes aware of them. SAEs occurring any time after the reporting period must be promptly reported if a causal relationship to the study drug is suspected.

# 10.2 Safety Reporting to Investigators, Institutional Review Boards or Independent Ethics Committees, and Regulatory Authorities.

Sponsor or its designee is responsible for reporting all applicable SAEs to Regulatory authorities, Investigators, and IECs/IRBs, as applicable, in accordance with national regulations in the countries where the study is conducted.

Suspected Unexpected Serious Adverse Reactions (SUSARs) should be reported as expedited safety reports to all participating Investigators, ethics committees, and applicable regulatory authorities in accordance with ICH guidelines and the local regulatory requirements. The SUSARs will be submitted within 7 days for fatal and life-threatening events and within 15 days for other SUSARs events.

The Sponsor should submit all safety updates and periodic reports to the regulatory authorities, as required by applicable regulatory requirements.

Investigators should report to their local IEC/IRB as dictated by their board's policies and procedures.

The blinding will be maintained for the team who are involved directly in the study. For SUSAR reporting, dedicated personnel may break the subject's code without revealing the blind to the Sponsor personnel, its designee or site team.

## 10.3 Pregnancy Reports

A female clinical trial subject must be instructed to inform the Investigator immediately if she becomes pregnant during the study. Pregnancies occurring up to 30 days after treatment discontinuation must also be reported to the Investigator.

The Investigator should report all pregnancies to Sponsor or its designee within 24 hours of becoming aware of them, using a clinical trial pregnancy reporting form.

All pregnancy reports will be captured in the safety database.

If the subject requests to know which treatment she received, this information will be provided to her (see Section 8.4.4).

The pregnancy should be followed for outcome of the mother and the child, including any premature terminations, and all outcomes should be reported to Sponsor or its designee.

[figure not shown]
#### 11 STATISTICAL METHODOLOGY

## 11.1 Open-Label Part

A total of 150 subjects, including those already randomized to Aramchol 300mg BID or placebo, will be randomized in a ratio of 1:1:1 to receive Aramchol 300mg BID according to the below grouping:

- Group A: The post-baseline liver biopsy will be conducted at week 24
- Group B: The post-baseline liver biopsy will be conducted at week 48
- Group C: The post-baseline liver biopsy will be conducted at week 72

Randomization in the Open-Label Part will employ a semi-minimization algorithm to balance the 3 groups in number of subjects, distribution of subjects according to fibrosis score (F1, F2 and F3), presence or absence of T2DM, and prior exposure to Aramchol 300mg BID. F1 subjects will be capped to enroll no more than 30 subjects.

[figure not shown]

## 11.2 Randomized, Double-Blind, Placebo-Controlled Part:

A total of 2000 subjects will be randomized into this study in a 2:1 ratio to treatment with Aramchol or with placebo, respectively.

An eligible subject will randomly be allocated to treatment with Aramchol or matching placebo based on a randomization scheme employing a 2:1 assignment ratio, respectively, using permuted blocks stratified by country/geographical region (CGR) and by baseline Fibrosis stage (F2 or F3).

## 11.2.2 Study Primary Endpoints

The primary efficacy endpoints for this study are:

- Histology-Based: The Histology-Based primary endpoint will be derived from the week-72 biopsy of the initial 1000 subjects as compared to baseline biopsy and will use:
  - ✓ Resolution of NASH defined as the Proportion (%) of subjects with resolution of NASH (defined by Ballooning of 0 and inflammation 0-1) and no worsening of liver fibrosis on NASH CRN fibrosis score (≥ 1 stage increase).

OR

[figure not shown]
✓ Improvement in Fibrosis defined as the Proportion (%) of subjects with improvement in liver fibrosis greater than or equal to one stage (NASH CRN fibrosis score) and no worsening of steatohepatitis (defined as no increase in NAS for ballooning, inflammation or steatosis)

[figure not shown]
- Clinically-Based: The Clinically-Based primary endpoint is the time to first occurrence of any of the following adjudicated events:
  - ✓ All-cause mortality
  - ✓ Liver transplant
  - ✓ Histological progression to cirrhosis
  - ✓ MELD score >15 if baseline MELD score was <12
    

  - ✓ Hospitalization due to hepatic decompensation event(s) including:
    - Hepatic encephalopathy grade ≥2 (as assessed by West Haven scale)
    - Variceal bleeding
    - New onset ascites requiring treatment
    - Spontaneous bacterial peritonitis as assessed by either positive cell culture or cell count

Events will be adjudicated by an independent adjudication committee.

[figure not shown]

## 11.2.7 Comparability of Study Groups at Baseline

Demographics and baseline data will be displayed for the ITT Analysis Set. Subjects' demographics and baseline characteristics, including baseline prognostic factors will descriptively be examined to assess the comparability of the treatment groups. For continuous variables, descriptive statistics (number [n], mean, standard deviation (SD), standard error, median, minimum, and maximum) will be provided. For categorical variables, subject counts and percentages will be provided. Categories for missing data will be presented.

Summary statistics of these parameters will also be provided when broken down by CGR, and by US/Non-US sub-populations.

## 11.2.8 Primary Estimands of Interest

## 11.2.8.1 Week-72 Histology-Based Primary Estimand

The primary Estimand for the Week-72 Histology-Based study part will be based on the effectiveness assumption (de-facto) using treatment policy. The primary Estimand construction elements of this Estimand are:

- Population: Subjects with Nonalcoholic Steatohepatitis (NASH) that were randomized to the study.
- Variables of interest: Week-72 (-2 Weeks, +6 Weeks) individual subject Resolution of NASH, OR, Improvement in Fibrosis.
- 3. Inter-current events: Subjects that ESD during the Histology-Based study part. The treatment-policy Estimand will be used to assess the benefit of Aramchol as compared to

- placebo in initially randomized subjects' as actually observed regardless of the occurrence of ESD during the Histology-Based study part.
- Population-level summary: The between groups difference in the proportion of subjects
  with NASH Resolution AND/OR the between groups difference in the proportion of subjects
  with Improvement in Fibrosis.

The treatment effect will be attributable to the subject's with NASH initially randomized to the study and who had the baseline and Week-72 liver biopsies regardless of ESD during the Histology-Based study part.

#### 11.2.8.2 EoS Clinically-Based Primary Estimand

The primary Estimand for the EoS Clinically-Based study part will be based on the effectiveness assumption (de-facto) using treatment policy. The primary Estimand construction elements are:

- Population: Subjects with Nonalcoholic Steatohepatitis (NASH) that were randomized to the study.
- 2. Variables of interest: Time to first occurrence of the adjudicated events.
- Inter-current event: Subjects that were early discontinued from the study (ESD). The
  treatment-policy Estimand will be used to assess the benefit of Aramchol as compared to
  placebo in initially randomized subjects' as actually observed regardless of the occurrence
  of ESD.
- 4. Population-level summary: The difference in survival distributions/percentiles observed in the Aramchol arm as compared to the Placebo Arm.

The treatment effect will be attributable to the subject's with NASH initially randomized to the study regardless of study early discontinuation.

#### 11.2.9 Efficacy Endpoints and Analyses

## 11.2.9.1 Primary Endpoints and Principal Analysis of the Study Primary Endpoints

The study identifies two primary endpoints: The Histology-Based endpoint and the Clinically-Based endpoint. The principal analysis sets for inference for these two primary endpoints will be the corresponding ITT Analysis Sets.

## 11.2.9.2 Principal Analysis of the Histology-Based Primary Endpoint

Within the work-frame of the Week-72 primary efficacy endpoint, the following two alternative outcome measures will be analyzed, separately, for assessing the efficacy of Aramchol as compared to placebo:

- Resolution of NASH
- Improvement in Fibrosis

The below described principal analysis will be conducted separately for **Resolution of NASH** and for **Improvement in Fibrosis**.

[figure not shown]
- The Histology-Based ITT Analysis Set (Histology-Based-ITT) will serve as the primary Analysis Set for efficacy assessment of the Histology-Based primary endpoint for the primary Estimand.
- Missing week 72 biopsy values will be handled concurrently by deterministic rules (e.g. subject who experience clinical events before week 72 will be considered treatment failures) and by multiple imputations procedures (MI).
- The analysis of the Histology-Based primary endpoint will be conducted using the imputed datasets and will employ the Cochran-Mantel-Haenszel (CMH) test (SAS® PROC FREQ) stratified by baseline Fibrosis stage (F2 or F3), baseline NAS score (<6 or ≥6), presence or absence of T2DM at baseline and country/geographical region (CGR).
- The Wilson-Hilferty transformation will be used to normalize the CMH test statistics and the Rubin's rule will be applied for combining the results to obtain the p-value.
- The magnitude of treatment effect estimate and its 95% CI will be calculated using the combined stratified difference in proportions using CMH weights.
- More details on imputation modeling and sensitivity analyses will be provided in the Statistical Analysis Plan (SAP).

### 11.2.9.3 Principal Analysis of the Clinically-Based Primary Endpoint

The Clinically-Based primary endpoint is the time to first occurrence of any of the following adjudicated events:

- All-cause mortality
- Liver transplant
- Histological progression to cirrhosis
- MELD score >15 if baseline MELD score was <12

- Hospitalization due to hepatic decompensation event(s) including:
  - ✓ Hepatic encephalopathy grade ≥2 (as assessed by West Haven scale)
  - √ Variceal bleeding
  - ✓ New onset ascites requiring treatment
  - ✓ Spontaneous bacterial peritonitis as assessed by either positive cell culture or cell count

[figure not shown]

[figure not shown]
## 11.2.10 Key Secondary Endpoint and Analysis

One key secondary endpoint, namely, 5-Year Proportion (%) of Subjects with Improvement in Fibrosis, is defined for the EoS Clinically-Based study part. This endpoint will be tested for the primary Estimand using the Clinically-Based-ITT Analysis Set.

The statistical methodology for the analysis of this endpoint will follow the one described for the Biopsy-Based primary endpoint and will be provided in detail in the SAP.

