### **Key Secondary Efficacy Endpoint:**

 At EoS, Improvement in Fibrosis: 5-Year Proportion (%) of subjects with improvement in liver fibrosis greater than or equal to one stage (NASH CRN fibrosis score) and no worsening of steatohepatitis (defined as no increase in NAS for ballooning, inflammation or steatosis)

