#### **Principal Analysis Set for Efficacy Inference:**

The principal analysis set for efficacy inference will be the Intention-to-Treat (ITT) Analysis Set which will include all randomized subjects as follows:

- The Histology-Based primary endpoint will employ the Histology-Based-ITT Analysis Set including all initially 1000 randomized subjects.
- The Clinically-Based primary endpoint will employ the Clinically-Based-ITT Analysis Set including all randomized subjects.

[figure not shown]

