# **Key Secondary Efficacy Endpoints**

The key secondary efficacy endpoint for the Randomized, Double-Blind, Placebo-Controlled Part is:

At EoS, **Improvement in Fibrosis:** 5-Year Proportion (%) of subjects with improvement in liver fibrosis greater than or equal to one stage (NASH CRN fibrosis score) and no worsening of steatohepatitis (defined as no increase in NAS for ballooning, inflammation or steatosis).

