#### Clinically-Based phase:

All 2000 subjects planned to be randomized into this study will receive Aramchol or matching placebo until End-of-Study (EoS) which will occur at the time when a total of 380 subjects will experience at least 1 pre-specified clinical event or at 5 years from last subject's randomization, whichever comes first.

Extension study: Subjects that complete 7 years in the study or that are ongoing at EoS will be provided the option to receive Aramchol treatment in an open-label extension. The extension study will be detailed under a separate protocol

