## Laboratory:

Fasting (8 hours) is required before the visit

- A urine pregnancy test in women of childbearing potential
- Complete blood count and serum biochemistry, Renal function (creatinine and eGFR), Coagulation, Thyroid function (TSH, T3 and T4), CPK, Glycemic parameters
- Blood sample for PK will be collected
- o Blood samples for potential biomarkers, metabolomics and better understanding of mechanism of action
- Drug accountability
- Liver biopsy will be conducted as follows
  - o In case the Sponsor announces EoS and the subject has not reached 5-year visit, it is recommended to perform a liver biopsy, unless there is an available biopsy within the past year.
  - There is no scheduled biopsy at year 7 visit

Coagulation results should be within normal ranges before the biopsy is performed. If the study subject is taking any anticoagulant it should be discontinued a sufficient amount of time before the biopsy to avoid any undue bleeding. NSAIDs are prohibited 48 hours prior to the biopsy.

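### Is the 5-year key secondary endpoint undefined for subjects who cannot reach year 5 if 380 events close the study first?

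*Combined protocol and SAP*

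**What the plan says.** The Synopsis words the key secondary as "At EoS, Improvement in Fibrosis: 5-Year Proportion (%) of subjects with improvement in liver fibrosis", and section 4.1.2 repeats it. Section 11.2.10 states that one key secondary endpoint, "namely, 5-Year Proportion (%) of Subjects with Improvement in Fibrosis, is defined for the EoS Clinically-Based study part", and tests it for the primary estimand in the Clinically-Based-ITT set. The Synopsis defines that set as follows: "The Clinically-Based primary endpoint will employ the Clinically-Based-ITT Analysis Set including all randomized subjects".

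Section 5.1 (Clinically-Based phase) ends the study when "380 subjects will experience at least 1 pre-specified clinical event or at 5 years from last subject's randomization, whichever comes first". Section 8.1 caps each subject at 7 years. Section 8.2.5 schedules the 5-year biopsy within 8 weeks either side of the 5-year visit.

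Section 8.2.6 foresees early closure: "In case the Sponsor announces EoS and the subject has not reached 5-year visit, it is recommended to perform a liver biopsy". It waives this biopsy if one exists from the past year.

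For the analysis, section 11.2.10 refers to the method of the biopsy-based primary endpoint and leaves the detail to the SAP. That method (section 11.2.9.2) combines deterministic rules with multiple imputation. Its one example of a deterministic rule is that a "subject who experience clinical events before week 72 will be considered treatment failures". Section 11.2.8.2 names only early study discontinuation as an intercurrent event. Under the Synopsis multiplicity rule, the key secondary is tested only if the clinical primary endpoint succeeds, at that endpoint's alpha of 0.03 or 0.05.

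**The concern.** The analysis set is everyone randomised, the endpoint carries a fixed time, and the closing date can fall before some subjects reach that time. If 380 events come first, analysis at EoS and measurement at year 5 are no longer the same moment for late entrants. Two analysts could then produce different data sets. One might count biopsies taken at closure, after varying durations, as 5-year results. The other might impute a 5-year result for every subject cut off by closure.

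This is the only secondary endpoint with alpha. Group-level week-72 results may be published while the study runs (section 8.4.3), so a rule chosen late would be chosen with related fibrosis results in view.

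**Working it through.** **Reading the two time labels.** The Synopsis list of exploratory endpoints uses the same construction: it first says when the analysis takes place (the histology analysis), then when the outcome is measured (week 72). Read the same way, the key secondary is analysed at EoS and measured at year 5. The labels do not contradict each other.

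**Which trigger comes first.** The figure of 380 (380/2000 = 19%) cannot be reproduced, because the sample-size section is not shown. Accrual time A, event rate h and dropout rate d are not visible either, so all three are assumed. With uniform accrual and constant rates:

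- Expected events at time T = 2000 × mean over entry e in [0, A] of h/(h+d) × (1 − exp(−(h+d)f)), where f = min(T − e, 7).
- EoS is the T that gives 380, or A + 5 if that is earlier.
- Share short of year 5 = 1 − (T − 5 + 8/52.18)/A, bounded to 0–1. The term 8/52.18 = 0.153 years is the early biopsy window.

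Example, A = 3, d = 3%, h = 5%: at T = 6.06, follow-up runs from 3.06 to 6.06 years. The mean of exp(−0.08f) is (0.7829 − 0.6158)/(0.08 × 3) = 0.696. Events = 2000 × (0.05/0.08) × 0.304 = 380. Share short = 1 − (1.06 + 0.153)/3 = 60%.

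Results for A = 3, d = 3%:

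| Events per year | EoS (years from first entry) | Short of year 5 | Follow-up of last subject (years) |
|---|---|---|---|
| 4% | 7.32 | 18% | 4.32 |
| 4.5% | 6.61 | 41% | 3.61 |
| 5% | 6.06 | 60% | 3.06 |
| 6% | 5.26 | 86% | 2.26 |

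Histological cirrhosis is found mainly at scheduled biopsies, so a constant rate brings EoS forward too much. If half of events surface only at week 72 and year 5, the shares are 0%, 9%, 27% and 51%. If three quarters do, they are 0%, 0%, 12% and 35%.

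Over A of 2 to 4 years and d of 0 to 5%, the calendar limit comes first below a threshold of 3.25% (A = 4, d = 0) to 4.12% (A = 2, d = 5%) per year.

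**The only rate in the documents.** Section 3.2 gives 52-week progression to cirrhosis of 1.3% on 600mg and 7.5% on placebo. Weighted 2:1, this is (2 × 1.3 + 7.5)/3 = 3.37%. At 3.4%, with A = 2/3/4, events at the calendar limit are 338/353/361 with 3% dropout and 320/333/340 with 5%. All are below 380, so closure leaves nobody short of year 5. With A = 3, d = 3% and clustered detection, the counts fall to 316 (half) and 297 (three quarters). With no dropout, at most 9% are short (A = 4).

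**What the carried-over method does.** A subject closed administratively has no year-5 biopsy, so the value is missing and goes to the deterministic rules or to imputation. Whether it is missing depends on the randomisation date and the date of the 380th event, not on the subject's own histology. Missing at random is a reasonable assumption there, and the week-72 biopsy is available as a predictor.

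**Whether substituting closure biopsies would help.** In the 6% row the last subject has 2.26 years of follow-up. The week-72 biopsy was taken at 72/52.18 = 1.38 years, so it is 2.26 − 1.38 = 0.88 years old at closure. Section 8.2.6 then waives a new one. A rule of year-5 biopsy, else closure biopsy, would still not say what counts for that subject.

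**The case for a change.** The strongest case for a change is that the protocol foresees closure before year 5 and recommends a biopsy then, yet no visible text says whether that biopsy, or the recent one that waives it, enters the endpoint or the imputation model. The cirrhosis rate of 3.4% probably understates the composite, which adds death, transplant, MELD and decompensation events. It also comes from another regimen and a population only 60% stage 2 or 3. The affected share moves from none to most over a narrow band of rates. At the extreme (A = 2, 6% per year, dropout of 3% or less) nobody reaches year 5, and imputation has no year-5 values to learn from.

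The open question about the closure biopsy stands, and so does the extreme case under its assumptions. But both concern detail that section 11.2.10 assigns to the SAP. Section 8.4.3 says that a SAP covering the EoS analyses was submitted before the study began and will be amended before the histology unblinding. Sections 11.2.3 to 11.2.6 and 11.2.12 are listed in the contents but not shown. The failure rule in section 11.2.9.2 is given only as an example, so a rule for closure is not excluded. That section 11.2.8.2 does not name closure carries little weight: sponsor closure is a missing-data matter, not an event in the subject's course.

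**Conclusion.** No change to the plan. The endpoint is a 5-year proportion, analysed at EoS. Where closure precludes the year-5 biopsy, the visible method leads by default to imputation, which suits this cause of missing data. No wrong result from following the plan has been shown. The share affected runs from 0% to 100% over assumed accrual of 2 to 4 years, dropout of 0 to 5% and event rates up to 6% per year. At the one documented rate, with 3% to 5% dropout, it is 0%.

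Redefining the endpoint around closure biopsies would not be a clear gain. It mixes treatment durations, replaces closure by entry date with possible self-selection into a biopsy that is only recommended, and leaves the waived case open. A supportive analysis in subjects randomised at least 5 years (less 8 weeks) before EoS would be clean, but may be small. With A = 3 and d = 3% it has about 809 subjects at 5% per year and 276 at 6%; with A = 2 at 6% it has none.

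The SAP authors can be asked to confirm, before the week-72 unblinding, how subjects closed before year 5 are handled and whether the closure biopsy, or the one that waives it, is used.
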